14.1.2 Fresh Tissue (Phase I part only)

- Autologous neoplastic B-cells derived from fresh tissue samples (lymph node biopsy specimen or organ specimen) will be exposed ex vivo to carfilzomib versus bortezomib +/- rituxan (including appropriate controls). Response to therapy will be measured. Additionally, genetic profiling (microarray), to determine activated B-cell (ABC) versus germinal B-cell (GBC) phenotype and protein profiling (protein arrays), in particular, changes in Bcl-2 family protein profile and/or inactivation of NF-κB signaling after ex vivo exposure of NHL cells to carfilzomib (compared to bortezomib), will be performed to examine potentially prognostic factors for response to C-R-ICE.

14.2 PK/PD Model Development

A pharmacologically-driven PK/PD model will be developed to elucidate the temporal relationship between carfilzomib concentrations and the time course of proteasome inhibition, along with temporal relationships with thrombocytopenia and neutropenia. This model will allow assessment of the dose and schedule at which carfilzomib facilitates maximal proteasome inhibition and thus lead to an increase response rate, while modulating the degree of severe toxicities. In addition, the effect of concomitant administration of rituximab, ifosfamide, carboplatin, and etoposide will be incorporated into the model to assess their potential effects on efficacy and/or toxicity.

First, a variety of compartmental population PK structural models will be evaluated to characterize the plasma concentration versus time profile following administration of carfilzomib using a nonlinear mixed effects modeling approach NONMEM®. The physiologic pharmacokinetic models explored will be described by the estimation of mean structural model

parameters (e.g. plasma volumes of distribution and clearances), the magnitude of inter-animal variability (IIV) in these parameters and the magnitude of residual variability (RV). For each model, the fit will be assessed by examination of several diagnostics. For comparisons of hierarchical models, the change in the minimum value of the objective function (MVOF), a statistic that is proportional to minus twice the log likelihood of the data, will be examined.

Using a sequential approach, a population PK/PD structural model will be developed for carfilzomib based on degree of proteasome inhibition in relation to efficacy and toxicity endpoints in the proposed study using NONMEM. This PK/PD model will describe the potential relationship between carfilzomib exposure in relation to proteasome inhibition to the time course of thrombocytopenia and neutropenia as indicators of pharmacodynamic response. The relationship between carfilzomib concentrations and these pharmacodynamic endpoints will be initially explored graphically and various structural models will be applied to the data and evaluated. Similar to the PK model development, criteria such as the precision of parameter estimates, magnitude of residual variability, and goodness-of-fit will be utilized for PK/PD model selection. The PK/PD model could be expanded to include attributes that are indicators of pharmacodynamic response from the concomitant medications of rituximab, ifosfamide, cisplatin, and etoposide which will modulate the overall response rate.

Assay for Proteasome Inhibition. This measures (but does not distinguish from) the activity of beta5 (constitutive proteasome) and LMP7 (immunoproteasome). Analysis of biomarkers that predict for response following treatment with proteasome inhibitors will also be performed on PBMC and whole blood plasma samples ((1) 10 ml green top tube with each blood draw) taken at time points below in Cycle 1 only: Day 1 of Cycle 1, pre-dose and 1 hr post end of infusion; Day 2 of Cycle 1, pre-dose and 1 hr post end of infusion and Day 3, Cycle 1, prior to rituximab administration..

Samples will be sent to Roswell Park Department of Medicine Lymphoma/Myeloma Laboratory for processing. Tube station #621 in Roswell Park Cancer Cell Center.

For additional information regarding the handling of samples please contact [name] at [contact] or [contact].

Furthermore, the final PK/PD model will be used to conduct a clinical trial simulation to predict pharmacokinetic outcomes of various dosing regimens (94, 95) to guide dosing and scheduling of C-R-ICE in relation to safety and efficacy endpoints. The simulation results will allow prediction of the exposure-response relationships for different doses and schedules of carfilzomib to achieve the desired responses.

15 ETHICAL AND REGULATORY STANDARDS

15.1 Ethical Principles

This study will not be initiated until the protocol and informed consent document(s) have been reviewed and approved by a properly constituted Institutional Review Board (IRB) or Independent Ethics Committee (IEC). Each subject (or legal guardian) shall read, understand, and sign an instrument of informed consent prior to performance of any study-specific

procedure. It is the responsibility of the investigator to ensure that the subject is made aware of the investigational nature of the treatment and that informed consent is given.

The Investigator is responsible for the retention of the subject log and subject records; although personal information may be reviewed by authorized persons, that information will be treated as strictly confidential and will not be made publicly available. The investigator is also responsible for obtaining subject authorization to access medical records and other applicable study specific information according to Health Insurance Portability and Accountability Act regulations (where applicable).

This study will be conducted in compliance with all applicable laws and regulations of the state and/or country and institution where the subject is treated, in accordance with the Declaration of Helsinki, Good Clinical Practice, and according to the guidelines in this protocol, including attached appendices.

15.2 Informed Consent

The Investigator is responsible for obtaining written consent from each subject or the subject's legally authorized representative in accordance with ICH-GCP guidelines using the approved informed consent form, before any study specific procedures (including screening procedures) are performed. The informed consent form acknowledges all information that must be given to the subject according to ICH-GCP, including the purpose and nature of the study, the expected efficacy and possible side effects of the treatment(s), and specifying that refusal to participate will not influence further options for therapy. Any additional information that is applicable to the study must also be included. Additional national or institutionally mandated requirements for informed consent must also be adhered to. The subject should also be made aware that by signing the consent form, processing of sensitive clinical trial data and transfer to other countries for further processing is allowed.

The Investigator shall provide a copy of the signed consent form to the subject and the signed original shall be maintained in the Investigator File. A copy of the signed consent form must be filed in the subject file. At any stage, the subject may withdraw from the study and such a decision will not affect any further treatment options.

16 STUDY RESPONSIBILITIES

16.1 Data Collection

Data entry into the database is to be completed in a timely fashion (approximately within 28 days) after the subject's clinic visit. If an AE is considered serious it is captured on both the Adverse Event page and the Serious Adverse Event Form, which is handled in an expedited fashion.

Data management activities will be performed using EXPeRT. EXPeRT is a suite of software tools that enables the collection, cleaning and viewing of clinical trial data. CRS data management will design the study-specific database and facilitate its development by the EXPeRT Information Technology team. Once the database design is approved by the Investigator, Statistician, and Clinical Research Coordinator, the database will be put into

production and data entry can begin. Data can be entered and changed only by those with the rights to do so into the eCRFs. EXPeRT is compliant with all relevant technical aspects of relevant GCP guidelines.

- The system can generate accurate copies of stored data and audit trail information in human readable form.
- System access is limited to authorized individuals through the controlled assignment of unique ID and password combinations.
- The system is designed to periodically force users to change their passwords and verifies that user ID and password combinations remain unique.
- The system automatically generates a permanent time-stamped audit trail of all user interactions.

When data entry is complete, data management will review the data and will query any missing, incomplete, or invalid data points for resolution by the Clinical Research Coordinator and Investigator. Once all queries have been resolved, the data can be released to the statistician for analysis.

16.2 Maintenance of Study Documents

Essential documents should be retained per Roswell Park policy for 6 years from the study termination date. These documents could be retained for a longer period, however, if required by the applicable local regulatory requirements or by an agreement with Roswell Park. It is the responsibility of Roswell Park to inform the Investigator/institution as to when these documents no longer need to be retained. If, for any reason, the Investigator desires to no longer maintain the study records, they may be transferred to another institution, another investigator, or to Roswell Park upon written agreement between the Investigator and Roswell Park.

17 ADMINISTRATIVE RULES

17.1 Revisions to the Protocol

Roswell Park may make such changes to the protocol as it deems necessary for safety reasons or as may be required by the U.S. FDA or other regulatory agencies. Revisions will be submitted to the IRB/ERC for written approval before implementation.

17.2 Termination of the Study

It is agreed that, for reasonable cause, either the Investigators or the Sponsor, Roswell Park may terminate this study, provided a written notice is submitted within the time period provided for in the Clinical Trial Agreement. In addition, Roswell Park may terminate the study at any time upon immediate notice if it believes termination is necessary for the safety of subjects enrolled in the study.

17.3 Confidentiality

Any data, specimens, forms, reports, video recordings, and other records that leave the site will be identified only by a participant identification number (Participant ID, PID) to maintain confidentiality. All records will be kept in a limited access environment. All computer entry and networking programs will be done using PIDs only. Information will not be released without written authorization of the participant.

18 APPENDICES

Appendix A. Ann Arbor Staging System

A staging system is a way for members of the cancer care team to summarize the extent of a cancer's spread. The staging system most often used to describe the extent of non-Hodgkin lymphoma in adults is called the Ann Arbor staging system.

The stages are described by Roman numerals I through IV (1-4). Lymphomas that affect an organ outside of the lymph system (an extranodal organ) have E added to their stage (for example, stage IIE), while those affecting the spleen have an S added.

Stage I

Either of the following means the disease is Stage I:

- The lymphoma is in only 1 lymph node area or lymphoid organ such as the thymus (I).
- The cancer is found only in 1 area of a single organ outside of the lymph system (IE).

Stage II

Either of the following means the disease is Stage II:

- The lymphoma is in 2 or more groups of lymph nodes on the same side of (above or below) the diaphragm (the thin band of muscle that separates the chest and abdomen). For example, this might include nodes in the underarm and neck area but not the combination of underarm and groin nodes (II).
- The lymphoma extends from a single group of lymph node(s) into a nearby organ (IIE). It may also affect other groups of lymph nodes on the same side of the diaphragm.

Stage III

Either of the following means the disease is Stage III:

- The lymphoma is found in lymph node areas on both sides of (above and below) the diaphragm.
- The cancer may also have spread into an area or organ next to the lymph nodes (IIIE), into the spleen (IIIS), or both (IIISE).

Stage IV

Either of the following means the disease is Stage IV:

- The lymphoma has spread outside of the lymph system into an organ that is not right next to an involved node.
- The lymphoma has spread to the bone marrow, liver, brain or spinal cord, or the pleura (thin lining of the lungs).

Other modifiers may also be used to describe the lymphoma stage:

Bulky Disease

This term is used to describe tumors in the chest that are at least one-third as wide as the chest, or tumors in other areas that are at least 10 centimeters (about 4 inches) across. It is usually designated by adding the letter X to the stage. Bulky disease may require more intensive treatment.

A vs. B

Each stage may also be assigned an A or B. The letter B is added (stage IIIB, for example) if a person has any of the B symptoms listed below:

- Loss of more than 10% of body weight over the previous 6 months (without dieting)
- Unexplained fever of at least 101.5°F
- Drenching night sweats

These symptoms usually mean the disease is more advanced. If a person has any of these, then more intensive treatment is usually recommended. If no B symptoms are present, the letter A is added to the stage.

Appendix B. Karnofsky Performance Status Scores

Definition	Score
Normal; no complaints; no evidence of disease	100
Able to carry on normal activity; minor signs or symptoms of disease	90
Normal activity with effort; some sign or symptoms of disease	80
Cares for self; unable to carry on normal activity or do active work	70
Requires occasional assistance, but is able to care for most personal needs	60
Requires considerable assistance and frequent medical care	50
Disabled; requires special care and assistance	40
Severely disabled; hospitalization is indicated, although death not imminent	30
Very sick; hospitalization necessary; active support treatment is necessary	20
Moribund; fatal processes progressing rapidly	10
Dead	0

Appendix C. Cockcroft-Gault Calculation for Creatinine Clearance

$$CrCL = \frac{[(140 - \text{Age}) * \text{Body Mass (in kg)}]}{[72 * \text{Serum Creatinine (in mg/dL)}]}$$

If the patient is female, multiply the above by 0.85. If the patient is obese (> 30% over ideal body weight), use ideal body weight in calculation of estimated CrCL.

2. INFORMED CONSENT

Informed consent must be obtained by the site Investigator/designee from any participants wishing to participate, prior to any study specific procedures.

An informed consent template is provided by RPCI and can be amended to reflect institutional requirements.

All consent changes must be reviewed by RPCI Network Office prior to submission to the site IRB.

The informed consent must be IRB approved.

Always check that the most up to date version of the IRB approved consent is being used.

Within 5 business days, notify the RPCI Network Office of all participant withdrawals or consent to limited study participation and appropriately document the discontinuation and the reason(s) why.

3. PARTICIPANT REGISTRATION

The participant completes the Gender, Race, and Ethnicity Form and this is placed in the study binder.

RPCI does not grant exceptions to eligibility criteria.

Phase 1 Protocol Registration Instructions

Contact the RPCI Network Monitor to verify that a slot is available in the open cohort when a participant has been identified. Do not have the participant sign consent prior to verifying an open slot.

- After the participant signs consent, the Subject Screening and Enrollment Log must be faxed or emailed to the RPCI Network Monitor within 1 business day. The RPCI Network Monitor will confirm receipt of the Subject Screening and Enrollment Log and email the participant ID number.
- When the participant has met eligibility, a signed eligibility checklist and other requested documentation will be faxed or emailed to the RPCI Network Monitor.
- Within 1 business day of receipt of the eligibility check list, the RPCI Network Monitor will fax or email the cohort assignment and dose level.
- An email must be sent by the site to confirm receipt of the cohort assignment and to provide the planned treatment start date.

4. STUDY DEVIATIONS

If a deviation has occurred to eliminate hazard, this must be reported to the RPCI Network, site IRB and any other regulatory authority involved in the study.

ALL study deviations will be recorded on the Study Deviation Log.

Participants inadvertently enrolled with significant deviation(s) from the study-specified criteria will be removed from the study, at the discretion of the Principle Investigator.

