4. METHODOLOGY

4.1. Study Design

This is an open-label, non-randomized, multicenter, dose-escalation Phase I, followed by Phase Ib expansion study of carfilzomib in combination with R-ICE regimen in relapsed/refractory DLBCL patients. Based on the results of the Phase I portion of the study, the Phase Ib dose will be at Dose Level 6. The study schema is depicted in **Figure 6**.

Figure 6. Treatment Plan Schema

Subjects will be treated on an inpatient and outpatient basis. All subjects will meet the inclusion and exclusion criteria summarized in **Section 5.1** and **Section 5.2** prior to enrollment in this study.

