4.2. Target Accrual and Study Duration

A maximum of 21 patients for Phase I and 9 patients for the Phase Ib expansion part of this trial will be enrolled at Roswell Park and Network Sites (For Phase Ib only). The number of subjects required is a function of a currently unknown dose-toxicity relationship. Accrual is expected to take up to 10 years.

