7.4.1.3 Criteria for Dose Escalation

Dose escalation will proceed within each cohort according to the following scheme in **Table 2**.

Patients who do not have a DLT and who do not complete Cycle 1 of treatment or more if appropriate will be replaced in the study.

Management and dose modifications associated with the above AEs are outlined in **Section 7.4**.

Table 2. Dose Escalation Scheme

Number of Patients with a Dose-Limiting Toxicity at a Given Dose Level	Escalation Decision Rule
0 out of 3	Enter 3 patients at the next dose level. If there are no dose-limiting toxicities found after completing all dose levels, an additional 3 patients will be enrolled at the maximally administered dose. If this dose level is determined to be a safe dose (≤ 1 out of 6 dose-limiting toxicities), it will then be used in the expansion phase.
≥ 2	Dose escalation will be stopped. This dose level will be declared the maximally administered dose (highest dose administered). Three additional patients will be entered at the next lowest dose level if only 3 patients were treated previously at that dose.
1 out of 3	Enter at least 3 more patients at this dose level. If 0 of these 3 patients experience a dose-limiting toxicity, proceed to the next dose level. If 1 or more of this group suffer a dose-limiting toxicity, then dose escalation is stopped, and this dose is declared the maximally administered dose. Three additional patients will be entered at the next lowest dose level if only 3 patients were treated previously at that dose.
≤ 1 out of 6 at highest dose level	This is generally the recommended Phase Ib dose. At least 6 patients must be entered at the recommended Phase Ib dose.

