13 STATISTICAL METHODOLOGY

This is single-center, open-label, prospective Phase I/Ib clinical trial evaluating the safety, efficacy, and pharmacokinetics/pharmacodynamics of carfilzomib and standard R-ICE combination therapy in adult patients with relapsed/refractory diffuse large B-cell lymphoma. The statistical design is based on a dose-finding algorithm to determine the maximal tolerated dose (MTD) of the study regimen and an assessment of the efficacy of the treatment for patients as compared to an external standard, i.e., R-ICE historical control. All enrolled patients will receive the study drug and initiation of the treatment should take place as soon as possible following study enrollment. A maximum total of up to 21 evaluable patients will be enrolled in the Phase I of this study, and a total of 9 evaluable patients will be enrolled in the Phase Ib portion of the study. An evaluable subject is defined as a subject who meets eligibility requirements and who does not discontinue prior to end of Cycle 1 for reasons other than DLTs for Phase I or who completes at least 1 cycle of planned therapy for Phase Ib. If a subject signs

an Informed Consent and does not receive treatment, the subject will not be classified as evaluable and will be replaced. Unevaluable patients will be replaced. Analyses will be performed with a focus on estimation of specific clinically important parameters for use in the planning of larger subsequent comparative trials designed to fully assess efficacy and safety.

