13.5.2 Phase Ib Decision Rules

Let π represent the proportion of the evaluable population of interest who experience an overall response within 3 weeks after completion of therapy (i.e., 3 cycles) at the carfilzomib MTD. If the response rate of less than 50% is considered unacceptable. A response rate of more than 70% is considered promising and evidence of such will deem the treatment worthy of further study. The null and alternative hypotheses corresponding to the design are

$$H_0 : \pi \leq 50\%,$$
$$H_a : \pi > 50\%.$$

A total of up to 30 evaluable patients will be accrued in the Phase I and Phase Ib portions of the study. The evaluable population is defined as patients who meet eligibility requirements and complete at least 1 cycle of therapy. Unevaluable patients will be replaced.

With this re-design, the probability is 4.8% of falsely concluding that the proportion of those who experience an overall response exceeds 50% and 80.1% is the probability of correctly concluding efficacy when the overall response rate is 70%.

In the event that the actual first stage sample size is not as planned, the adjustment of the first-stage stopping rule will be based on the approximate minimax rule proposed in Green and Dahlberg (1992): Stop the trial if the number of responses is α or less, where α is the largest value for which power properties would be maintained given the attained first-stage sample size, assuming the planned final sample size is achieved and one applies the planned final boundary. If the planned second stage sample size is not attained, the bound will be adjusted so to preserve Type I error.

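### A treated non-responder can be ruled ineligible late and replaced: response evaluability depends on eligibility, no deadline applies, and the sections disagree on whether treated or evaluable patients are counted

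*Combined protocol and SAP*

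**What the plan says.** - **Appendix E, section 4 (network-site instructions):** "Participants inadvertently enrolled with significant deviation(s) from the study-specified criteria will be removed from the study, at the discretion of the Principle Investigator." It does not define a significant deviation, set a time limit or name a decision-maker unaware of outcome. It does require every deviation to be logged.
- **Section 13:** "An evaluable subject is defined as a subject who meets eligibility requirements". The further condition is not leaving before the end of Cycle 1 for a reason other than a DLT (Phase I), or completing at least one cycle (Phase Ib). Then: "Unevaluable patients will be replaced."
- **Section 13.5.2 (response test):** "The evaluable population is defined as patients who meet eligibility requirements and complete at least 1 cycle of therapy. Unevaluable patients will be replaced."
- **Which set is analysed:** Section 13.1.2 pools evaluable patients from both phases. Section 13.5 instead says that the efficacy analysis covers the patients treated in both phases.
- **Setting:** Section 4.1 begins: "This is an open-label, non-randomized, multicenter, dose-escalation Phase I". Section 4.2 limits network sites to Phase Ib, which adds 9 patients.

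**The concern.** Eligibility is normally settled before treatment. Here a ruling of ineligibility can come at any time, including after the response scans, and its consequence is that the patient drops out of the response count and a new patient takes the place. Some entry criteria rest on judgement. Section 5.1.2, for example, leaves significant toxicity from prior treatment to the investigator's discretion, so a late ruling need not be mechanical.

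This route differs from early dropout because it can reach a patient who completed all three cycles and was scanned. If rulings fall more often on non-responders, the response rate is biased upward. The comparison is with a fixed 50%, so no control arm shares the bias.

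**Working it through.** **Inputs.** N = 30 evaluable, null rate 50%, alternative 70%, stated type I error 4.8% and power 80.1% (Section 13.5.2); 9 Phase Ib patients (Section 4.2). Assumptions: the success cutoff, the number or share of non-responders removed, and that no responder is removed.

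**1. The plan's own figures.** Let X be the number of responders in 30. Exact binomial:
- at least 19 of 30: P(X ≥ 19 | 0.5) = 10.0%, power at 70% = 84.1%
- at least 20 of 30: P(X ≥ 20 | 0.5) = 4.94%, power at 70% = 73.0%

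The stated pair is not reproduced at 30 patients. That is a separate matter. At least 20 of 30 is the lowest cutoff that keeps the error under 5%, so it is used below.

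**2. A few known non-responders removed, each replaced once.** At a true rate of 50%, P(X = 19) = 0.0509, P(X = 18) = 0.0806 and P(X = 17) = 0.1115. A replacement responds with probability 0.5.
- One removed: 0.0494 + 0.0509 × 1/2 = 0.0748, or 7.5%
- Two removed: 0.0494 + 0.0509 × 3/4 + 0.0806 × 1/4 = 0.1077, or 10.8%
- Three removed: 0.0494 + 0.0509 × 7/8 + 0.0806 × 4/8 + 0.1115 × 1/8 = 0.1481, or 14.8%

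If only the 9 Phase Ib patients can be removed, one removal still gives about 7.5%, because those 9 almost always include a non-responder (1 − 0.5⁹ = 0.998).

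**3. A fixed share q of non-responders removed and replaced.** The apparent rate is p′ = p / [p + (1 − p)(1 − q)] with p = 0.5. With all 30 exposed, the error is P(X ≥ 20 | 30, p′). With only Phase Ib exposed, X is the sum of a binomial(21, 0.5) and a binomial(9, p′).

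| q | p′ | Type I error, all 30 exposed | Type I error, 9 exposed |
|---|---|---|---|
| 0 | 0.500 | 4.94% | 4.94% |
| 5% | 0.513 | 6.55% | 5.4% |
| 10% | 0.526 | 8.65% | 5.9% |
| 20% | 0.556 | 14.9% | 7.1% |

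At q = 10% the expected observed response rate is 52.6% with all 30 exposed. With 9 exposed it is (21 × 0.5 + 9 × 0.526) / 30 = 50.8%.

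**4. Scale.** At a true rate of 50%, about 15 of 30 patients are non-responders, so 10% is 1.5 patients. Among 9 patients about 4.5 are non-responders, so 20% is 0.9 of a patient.

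**The case against.** **Appendix E does not itself change the denominator.** It mentions neither analysis sets nor replacement. Under Sections 13 and 13.5.2 an ineligible patient is unevaluable whether or not removed, and an eligible patient who completed a cycle stays evaluable even if removed. This stands. The exclusion comes from Section 13; Appendix E shows that the judgement can be discretionary and late.

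**Few patients may be exposed.** The Appendix E clause addresses network sites, hence at most the 9 Phase Ib patients. This stands for that clause and is why the smaller column is shown. The eligibility and replacement wording in Section 13 applies at every site.

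**Controls exist.** Appendix E grants no eligibility exceptions and requires a signed checklist before cohort assignment, pathology is reviewed centrally, and all deviations are logged. Removal needs a real deviation; non-response alone does not qualify. These controls make removals rarer and traceable, but they do not keep the patient in the count.

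**The test may not be close.** Section 13.1.2 reports a 90% response rate in Phase I, so a borderline result is less likely. However, Section 13 gives estimation for later trials as the focus, and the estimate carries the same bias.

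**Two stronger readings fail.** A reader might infer that removed patients vanish from the safety data. Sections 8.5, 11.1.3, 11.2.2 and 11.4 collect and follow adverse events without reference to evaluability. A reader might also infer that DLTs can be removed from the escalation counts. Section 7.4.1.3 says: "Patients who do not have a DLT and who do not complete Cycle 1 of treatment or more if appropriate will be replaced", so it provides no replacement for a patient with a DLT. Network sites do not enrol in Phase I under Section 4.2, and Section 4.1 says the Phase Ib dose is already set. What remains is a wording gap: Section 13 makes eligibility a condition of Phase I evaluability without excepting patients who had a DLT.

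**Conclusion.** The point holds for the response endpoint. Evaluability tied to eligibility, replacement, an undated discretionary judgement and open-label outcomes together let a known non-responder leave the denominator. The treated-patient wording in Section 13.5 would prevent this, but Sections 13.1.2 and 13.5.2 contradict it.

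One or two such removals move type I error from 4.9% to about 7.5% or 10.8%. With a fixed 5% to 20% of non-responders removed, it is 6.55% to 14.9% if all 30 patients are exposed, or 5.4% to 7.1% if only the 9 Phase Ib patients are. All of this assumes a cutoff of 20 of 30, a true rate of 50% and one-sided removal. The documents give no removal rate, and nothing in them shows that outcome-driven removal has happened or is intended. This is an inexpensive improvement to make, with no claim about safety data and only a reconciliation request on DLTs.

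**What to change.** 1. In Sections 13, 13.1.2 and 13.5.2, adopt the treated-patient set of Section 13.5 for the primary response analysis: every patient who received study drug counts. Because Section 13.2 rules out imputation, also say how a treated patient without a response assessment is classified.
2. In Appendix E, section 4, state that removal concerns continued protocol treatment only. It does not take data out of any analysis or end follow-up.
3. If an eligible-only analysis is kept, make it a sensitivity analysis. Eligibility should be ruled on from baseline data before the first restaging scan, which Section 10.2 places between Cycle 2 Day 15 and Day 28.
4. Reconcile the Phase I evaluability wording in Section 13 with the replacement rule in Section 7.4.1.3.

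The cost is a few sentences. The downside is that a few ineligible patients may slightly dilute the response rate; the sensitivity analysis would show by how much.
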